9.2 Analysis Sets

Primary endpoint components

The analysis set will include all expert curators and patient participants and will take into account the primary data points (PDP) identified in yellow in the figure below across the 3 arms.

Primary Data Point	Generation	Arm	Description of measures (through RedCap Form and computed)		
PDP1	G0		M2.1 : Estimated time spent in curation per patient record (min)		
PDP2	G1	Expert Curator	M1: System Usability Score M2.1: Estimated time spent in curation per patient record (min)		
PDP3	G2		Same than for G1 - measured for G2		
PDP4	G1	G1 AND G2 users	 M1: System Usability Score M2: Time spent in for curation in min Estimated time in RedCap form (M2.1) Computed "active" time to answer queries (M2.2) Computed amount of data elements curated automatically by system (M2.3) requiring human intervention with answer from the patient (M2.4) 		

Primary Data Point	Generation	Arm	Description of measures (through RedCap Form and computed)
			 without answer the patient and requiring curator input (M2.5) without answer requested from curator but not successful (M2.6)
			M3: Computed data quality scores of curated record in terms of completeness, correctness, consistency and trustworthiness (as detailed in Task 4.6).
			 M4: Computed quality of the NLP concept extraction against the manually annotated data ("gold standard") Precision (M4.1) which measures the fraction of gold standard instances among the retrieved instances Recall (M4.2) which measures the fraction of the gold standard concepts that could successfully be retrieved
PDP5	G2		Same than PDP4 - for G2
PDP6	G1	G1 OR G2	Same than PDP4 - for G1
PDP7	G2	users	Same than PDP5 - for G2

Secondary endpoints

The analysis set will include all data users (BC specialists and CVD experts) and will take into account the secondary data points (SDP) identified in orange in the figure below across the patient arms. As indeed this is about reuse of data, after the curation process; there is no effect expected from the fact that patients did use G1 before G2 or not.

Secondary Data Point	Generation	Arm	Description of measures (through RedCap Form and computed)		
			Breast Cancer		
SDPO	GO	With ± 15 patients on site	 EBCx: estimated total effort (person min, person hours or person days) for BC specialist and supporting local team to answer the queries (BC1, BC2, BC3 described in Section 3.2.1) across sites TBCx: estimated duration (min, hours or days) for the BC specialist to have an answer to the queries (BC1, BC2, BC3) across sites. Duration = time between the first request and the time the answer is provider 		
SDP1	G1	All patients	 EBCx: total effort for BC specialist (and local team) to answer the queries (BC1, BC2, BC3) across sites TBCx: duration (min, hours or days) for the BC specialist to have an answer to the queries (BC1, BC2, BC3) across sites. HBCx: answer to the query as provided by human BC specialist ABCx: answer to the query as computed by AIDAVA ACCx: accuracy of calculation by AIDAVA compared to BC specialist 		
SDP2	G2		Same than SDP1 - for G2		
		1	CVD		
SDP1	G1	All patients	 CVD. SMART risk score computed by AIDAVA TCVD1.1/TCVD1.2. Time required for the treating/ senior physician to compute the SMART score (collect + analyse + enter data into a standalone web page calculator) CVD1.1/CVD1.2. SMART score computed by treating / senior physician ACVD1.1/ACVD1.2. Accuracy of automatic calculation of the score compared to treating/senior physician-entered score 		
SDP2	G2		Same than SDP1 - for G2		

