9.1 Statistical Hypotheses

The primary objective is to demonstrate that G1 of the AIDAVA prototype is superior to the current situation in achieving data curation and publishing of personal health data; and that G2 is superior to G1. Improved efficiency will be measured through 4 endpoints i.e. M1 (usability of the tool), M2 (decreased time to curated data), M3 (high quality of resulting data), M4 (extraction of structured data from text).

- The 2 critical metrics are M2 (time) and M3 (quality).
- While important, **M1 (usability)** should be possible to improve (more training, increased explanation, ..) and the results of the evaluation will provide directions on how to improve.
- M4 (NLP performance) will improve with the introduction of new technologies (Large Language Models like ChatGPT and BARD) and is therefore less critical for the future of AIDAVA.

Thus, the null hypothesis to be tested in relation to the **primary estimand**¹⁷ is as follows.

• Null hypothesis (H0): The efficiency of data curation and publishing of personal health data is not different between G1 or G2 of the AIDAVA prototype and the current situation. There is no impact due to training on data curation.

vs.

- Alternative hypothesis (H1):
 - G1 of the AIDAVA prototype is more effective than the current situation with respect to the efficiency of data curation and publishing of personal health data and G2 is even more effective than G1.
 - The efficiency improvement is due mainly to the tool; some improvement is related to the training on data curation.

The null and alternative hypotheses corresponding to the secondary estimands are as follows:

Secondary objective for Breast Cancer Use Case:

- Null hypothesis: There is no difference with AIDAVA, to get an answer to specific queries on the BC registry across sites, in terms of accuracy and time.
- Alternative hypothesis (H2-BC): AIDAVA G1 provides correct answers on queries on the BC registries across sites (with an accuracy 90% or higher), while avoiding BC specialists (and supporting team) to spend time. G2 has similar or better results.

¹⁷ estimand (trial objective) is the target of estimation. In AIDAVA, the primary estimand is improved efficiency in data curation

Secondary objective for CVD specialists :

- Null hypothesis: There is no difference to compute SMART score for patients across sites, in terms of accuracy and time with AIDAVA.

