9.3 Statistical Analyses

Three tests have be retained

- **Paired t-test**: statistical test that compares the means of two related groups, where each subject is measured at two different time points or under two different conditions. It is used to determine if there is a significant difference between the two groups.
- Mann-Whitney U test (unpaired t-test): non-parametric statistical test used to compare the medians of two independent groups. It is often used when the data are not normally distributed or when the sample sizes are small.
- Wilcoxon signed-rank test: non-parametric statistical hypothesis test used to compare two populations with two matched samples.

Primary Endpoint(s) Analysis

The endpoints are defined in Section 9.2 will be used to support the analysis

Computed	Description of measures	Test & meaning (per H1)			
	Population: Expert Curators				
E1	Difference between data points 1 and 2: E1.M2.1△ = M2.1@PDP1 - M2.1@PDP2 E1.M2.2△ = M2.2@PDP1 - M2.2@PDP2	Paired t-test H1: less time spent in curation in G1 than in G0 for expert curators			
E2	Difference between data points 2 and 3: E2.M1-Δ = M1@PDP2 - M1@PDP3	Paired t-test H1: G2 is more usable than G1 for expert curators			
	E2.M2.1∆ = M2.1@PDP2 - M2.1@PDP3 E2.M2.2∆ = M2.2@PDP2 - M2.2@PDP3	H1: less time spent in curation in G2 than in G1 for expert curators			
	Population:	Patients			
P1	Difference in data points 4 and 5 (i.e. difference between G1 and G2 for arm where patients used G1 AND G2)	Paired t-test (effect of system + training/experience from G1)			
	P1.M1- = M1@PDP4 - M1@PDP5	H1: G2 more usable than G1			
	P1.M2.x∆ = M2.x@PDP4 - M2.x@PDP5	H1: G2 requires less time for curation than G1 H1: G2 enables curation with less human intervention than G1			
	P1.M3-∆ = M3@PDP4 - M3@PDP5	H1: G2 provide same or higher quality than G1			
P2	Difference in data points 6 and 7 (i.e. difference between G1 and G2 for arm where patients used G1 OR G2)	Unpaired t-test (effect of system only)			
	P2.M1- = M1@PDP6 - M1@PDP7	H1: G2 more usable than G1			
	P2.M2.x∆ = M2.x@PDP6 - M2.x@PDP7	H1: G2 requires less time for curation than G1 H1: G2 enable curation with less human intervention than G1			
	Ρ2.Μ3-Δ = M3@PDP6 - M3@PDP7	H1: G2 provide same or higher quality than G1			

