A1	Sum across patient arms for G1 A1.M1 = M1@PDP4 + M1@PDP6 A1.M2.x = M2.x@PDP4 + M2.x@PDP6 A1.M3.x = M3.x@PDP4 + M3.x@PDP6 A1.M4.x = M4.x@PDP4 + M4.x@PDP6	Descriptive Statistics Performance in G1 of the AIDAVA system.			
A2	Sum across patient arms for G2	Descriptive Statistics			

Computed	Description of measures	Test & meaning (per H1)
	A2.M1 = M1@PDP5 + M1@PDP7 A2.M2.x = M2.x@PDP5 + M2.x@PDP7 A2.M3.x = M3.x@PDP5 + M3.x@PDP7 A2.M4.x = M4.1@PDP5 + M4.x@PDP7	Performance in G2 of the AIDAVA system.
A3	Difference in A1 and A2 (i.e. difference between G1 and G2 across all patients)	Unpaired t-test
	Α3.Μ1-Δ = Α1.Μ1 - Α2.Μ1	H1: G2 more usable than G1
	A3.M2.xΔ = A1.M2.x - A2.M2.x A3.M3.x-Δ = A1.M3.x - A2.M3.x	H1: G2 requires less time for curation than G1 H1: G2 enable curation with less human intervention than G1
	A3.M4.X-∆ = A1.M4.x - A2.M4.x	Wilcoxon signed-rank test H1: The NLP system developed in G2 yields a higher precision than the NLP system from G1. H1: The NLP system developed in G2 yields a higher recall than the NLP system from G1.
A4	Difference in P1 and P2 (difference between the 2 patient arms)	Unpaired t-test (effect on training/experience) There is a difference in performance due to training/experience with the system : patients having used G1 are more/not more effective in G2 than patients who work with only one generation of the prototype (G1 or G2)
	Α4.Μ1-Δ = P1.Μ1-Δ - P2.Μ1-Δ	H1: G2 more usable than G1 (due to experience during G1)
	A4.M2.x-Δ = P1.M2.x-Δ - P2.M2.x-Δ A4.M3.x-Δ = P1.M3.x-Δ - P2.M3.x-Δ	H1: G2 requires less time for curation than G1 as patients are more experienced H1: There are less questions of the system unanswered during G2 than in G1 as the patient acquired experience in G1
	A4.M4	Not useful

Secondary Endpoint(s) Analysis

Description of measures	Test & meaning (per H1)
Breast Canc	er
Difference in data points 0 and 1 (i.e. difference between G0 and G1 across a sample of 15 patients) U0.TBCx- Δ = TBCx@SDP0 - TBCx@SDPA U0.EBCx- Δ = EBCx@SDP0 - EBCx@SDP1 U0.ACCx- Δ = ACCx@SDP0 - ACCx@SDP1	Unpaired t-test H1: G2 has more (or same) accuracy than G1 while keeping the same time saving and duration
	Descriptive Statistics around performance in G1 of the AIDAVA system (e.g. mean,)

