Difference in data points 1 and 2 (i.e. difference between G1 and G2 across all patients) U1.TBCx- Δ = TBCx@SDP1 - TBCx@SDP2 U1.EBCx- Δ = EBCx@PSP1 - EBCx@SDP2 U1.ACCx- Δ = ACCx@SDP1 - ACCx@SDP2	Paired t-test H1: G2 has more (or same) accuracy than G1 while keeping the same time saving and duration
Cardiovascu	lar
	Descriptive Statistics around performance in G1 of the AIDAVA system (e.g. mean,)
Difference in data points 1 and 2 (i.e. difference between G1 and G2 across all patients) U1.TCVD- Δ = TCVD@SDP1 - TCVD@SDP2	Paired t-test H1: G2 has more (or same) accuracy than G1 while keeping the same time saving
	Description of measures Breast Canc Difference in data points 0 and 1 (i.e. difference between G0 and G1 across a sample of 15 patients) U0.TBCx- Δ = TBCx@SDP0 - TBCx@SDPA U0.EBCx- Δ = EBCx@SDP0 - EBCx@SDP1 U0.ACCx- Δ = ACCx@SDP0 - ACCx@SDP1 Difference in data points 1 and 2 (i.e. difference between G1 and G2 across all patients) U1.TBCx- Δ = TBCx@SDP1 - TBCx@SDP2 U1.EBCx- Δ = EBCx@PSP1 - EBCx@SDP2 U1.ACCx- Δ = ACCx@SDP1 - ACCx@SDP2 Cardiovascu Difference in data points 1 and 2 (i.e. difference between G1 and G2 across all patients) U1.TCVD- Δ = TCVD@SDP1 - TCVD@SDP2 U1.ACCyD- Δ = ACVD@SDP1 - ACVD@SDP2 U1.ACCyD- Δ = ACVD@SDP1 - ACVD@SDP2

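### For CVD scoring accuracy, the paired G1-G2 contrast U1 can credit patients' G1 experience to G2, because Section 9.2 assumes without support that prior use has no effect

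*Protocol*

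**What the plan says.** All references are to the Protocol.

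- **Section 9.2, secondary endpoints.** The analysis covers all patients without a split by arm. The reason given is "As indeed this is about reuse of data, after the curation process", and the conclusion is that "there is no effect expected from the fact that patients did use G1 before G2 or not".
- **Section 9.1, H1 for the primary estimand.** The gain is mainly due to the tool, but "some improvement is related to the training on data curation".
- **Section 9.3, P1.** The paired G1-G2 test in patients who used both generations is labelled "effect of system + training/experience from G1". P2, in single-generation patients, is labelled as the system alone.
- **Section 9.3, A4.** The difference between P1 and P2 is used to test whether "There is a difference in performance due to training/experience with the system". It lists a data-quality term, "A4.M3.x-Δ = P1.M3.x-Δ - P2.M3.x-Δ", and one of its hypotheses is that "There are less questions of the system unanswered during G2 than in G1 as the patient acquired experience in G1".
- **Section 9.3, U1 for CVD.** A paired t-test on "Difference in data points 1 and 2 (i.e. difference between G1 and G2 across all patients" is read as G2 having at least the accuracy of G1. It has no experience label, no split by arm and no counterpart of A4.
- **Section 9.2, CVD data points.** ACVD compares the automatic SMART score with the physician's score, patient by patient.

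**The concern.** Coming after curation does not make a measure independent of curation. The SMART score takes the curated record as its input. If G1 experience makes a patient a better curator at G2, the record can be better and the automatic score can lie closer to the physician's, with no improvement in the tool.

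The protocol allows for this in the primary analysis by running P1, P2 and A4 side by side. In the secondary analysis it sets the issue aside by assumption and keeps only the paired contrast. At stake is the part of H2-CVD that says G2 has similar or better accuracy than G1. It would be read as a property of the system when the contrast cannot separate system from experience.

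**Working it through.** The point rests on no figure stated in the plan, so the check sets the passages side by side and then illustrates what follows.

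**1. Is there a route from patient experience to ACVD?**
- Section 2.2, Step 2: the graph is built automatically, with questions to the patient or the curator where automation fails.
- Section 2.2, Step 3b: the SMART inputs are extracted from that graph.
- Section 2.3: a wrong patient answer may introduce errors into the record.
- Section 3.2.2: several missing inputs are replaced by a population or default value, so completeness of the record can also change the score.
- Section 4.4.4: at G2, returning patients load all their data afresh and curate again.

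The route exists. Nothing in the documents shows how strong it is.

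**2. Who can contribute to U1 for CVD?** ACVD is a patient-level measure. A patient-paired test needs a G1 and a G2 value from the same person, so single-generation patients contribute nothing. Section 7.2 allows new recruits for the second evaluation, and they would fall outside U1. The all-patients description and the paired test therefore do not fit together.

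**3. What does U1 estimate?** Write the accuracy gain as G2 minus G1 (the protocol's Δ has the opposite sign), with s the system effect and e the effect of the patient's earlier use.
- Paired, returning patients: expected gain = s + e. This is the protocol's own reading of P1.
- First-time G2 patients against G1 patients: expected gain = s as far as patient experience is concerned, because every G1 patient is a first-time user at G1.
- The first minus the second gives e, the logic of A4.

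U1 supplies only s + e.

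**4. What could that do to the test?** This is illustration only. It uses a paired t-test at two-sided 5% (the protocol states no alpha) with s = 0. The value of e, in standard deviations of the paired difference, and the number n of returning CVD patients are both assumed. The target is 15 × 3 sites = 45 CVD patients, so n = 45 means that everyone returns. The noncentrality is e × √n.

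| n returning | e = 0 | e = 0.1 | e = 0.2 | e = 0.3 |
|---|---|---|---|---|
| 25 | 5% | 8% | 16% | 30% |
| 40 | 5% | 10% | 24% | 46% |
| 45 | 5% | 10% | 26% | 50% |

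The entries are the chance of a significant G1-G2 difference when the tool itself has not changed. If e is zero there is no distortion.

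**5. Does the same hold for breast cancer accuracy?** No. In Sections 3.2.1 and 9.2, ACCx compares the answers to a query that is consolidated across sites. It is not a patient-level value, first-time G2 patients enter the registry, and any pairing must be by query, site or specialist.

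**The case against.** **The effect may be negligible.** Questions that the patient cannot answer go to an expert curator (Section 3.1, M2.5), so experience may change who answers, or how long it takes, without changing the final record. Many SMART inputs are coded diagnoses, laboratory values, medication or demographics. Returning patients are retrained, and 16 to 18 months separate the generations. All of this stands. It is why the point is that U1 can credit experience to G2, and not that it does.

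**There is no flat contradiction.** A reader might infer that Section 9.2 contradicts H1 and A4 outright. The documents do not support that. H1's training clause and A4 belong to the primary endpoints. A4 lists a data-quality difference, but its written hypotheses concern usability, time and unanswered questions. Section 9.2 also gives a reason. What remains is an unsupported assumption, inconsistent with how the same mechanism is treated upstream.

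**The sentence is reasonable for some endpoints.** It also covers specialist and physician time, where no effect of the patient's prior use is plausible. Deleting it altogether would overcorrect.

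**The remedy is imperfect.** Curators assess both generations, so first-time G2 records are curated with help from experienced curators. Returning CVD patients also carry a longer record and further home blood pressure data, so comparing them with first-time patients at G2 mixes experience with record content. Both objections stand and limit how the added comparison may be described. They do not make U1 alone a better answer.

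**Conclusion.** The point holds for ACVD only, as a minor and inexpensive correction. A patient-paired U1 estimates system plus patient experience in returning patients, but the plan reads it as G2 against G1 in all patients. An experience effect enters in full. Its size cannot be derived from the documents, and the percentages above rest wholly on assumed values of e and n.

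Two wider inferences are not supported:
- **Breast cancer accuracy.** Its U1 is also called a paired test, but the unit is the query answer, so the argument about returning patients does not transfer.
- **A number for the bias from Section 9.4.** The 50 to 80 subjects given there are a number assumed sufficient, not a number expected to return. They yield no share of returning patients.

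The numeric criterion of at least 80% SMART accuracy at G1 is unaffected, since every patient is a first-time user then. Only the statement that G2 is similar or better is affected.

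**What to change.** 1. In Section 9.2, limit the no-effect sentence so that it does not cover ACVD. It may stand for specialist and physician time.
2. In Section 9.3, label the CVD accuracy U1 as system plus training/experience, as P1 already is, and state that it covers returning patients only.
3. Split CVD data point SDP2 by arm, as PDP5 and PDP7 do, and report ACVD at G2 for each arm.
4. Beside U1, report ACVD for first-time G2 patients against G1 patients with an interval. Describe it as free of patient experience only: curators return, and the comparison is between different, non-randomised people.

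**Cost.** A reworded sentence, a label and an extra table row; the arms are already defined and no new data are needed. The first-time G2 group depends on replacement recruitment and may be small or empty, so its interval may be wide. If it is empty, the label in step 2 is still needed, and system and experience cannot be separated.

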9.3 Statistical Analyses

Three tests have be retained

- **Paired t-test**: statistical test that compares the means of two related groups, where each subject is measured at two different time points or under two different conditions. It is used to determine if there is a significant difference between the two groups.
- Mann-Whitney U test (unpaired t-test): non-parametric statistical test used to compare the medians of two independent groups. It is often used when the data are not normally distributed or when the sample sizes are small.
- Wilcoxon signed-rank test: non-parametric statistical hypothesis test used to compare two populations with two matched samples.

Primary Endpoint(s) Analysis

The endpoints are defined in Section 9.2 will be used to support the analysis

Computed	Description of measures	Test & meaning (per H1)			
	Population: Expert Curators				
E1	Difference between data points 1 and 2: E1.M2.1△ = M2.1@PDP1 - M2.1@PDP2 E1.M2.2△ = M2.2@PDP1 - M2.2@PDP2	Paired t-test H1: less time spent in curation in G1 than in G0 for expert curators			
E2	Difference between data points 2 and 3: E2.M1-Δ = M1@PDP2 - M1@PDP3	Paired t-test H1: G2 is more usable than G1 for expert curators			
	E2.M2.1∆ = M2.1@PDP2 - M2.1@PDP3 E2.M2.2∆ = M2.2@PDP2 - M2.2@PDP3	H1: less time spent in curation in G2 than in G1 for expert curators			
	Population:	Patients			
P1	Difference in data points 4 and 5 (i.e. difference between G1 and G2 for arm where patients used G1 AND G2)	Paired t-test (effect of system + training/experience from G1)			
	P1.M1- = M1@PDP4 - M1@PDP5	H1: G2 more usable than G1			
	P1.M2.x∆ = M2.x@PDP4 - M2.x@PDP5	H1: G2 requires less time for curation than G1 H1: G2 enables curation with less human intervention than G1			
	P1.M3-∆ = M3@PDP4 - M3@PDP5	H1: G2 provide same or higher quality than G1			
P2	Difference in data points 6 and 7 (i.e. difference between G1 and G2 for arm where patients used G1 OR G2)	Unpaired t-test (effect of system only)			
	P2.M1- = M1@PDP6 - M1@PDP7	H1: G2 more usable than G1			
	P2.M2.x∆ = M2.x@PDP6 - M2.x@PDP7	H1: G2 requires less time for curation than G1 H1: G2 enable curation with less human intervention than G1			
	Ρ2.Μ3-Δ = M3@PDP6 - M3@PDP7	H1: G2 provide same or higher quality than G1			
A1	Sum across patient arms for G1 A1.M1 = M1@PDP4 + M1@PDP6 A1.M2.x = M2.x@PDP4 + M2.x@PDP6 A1.M3.x = M3.x@PDP4 + M3.x@PDP6 A1.M4.x = M4.x@PDP4 + M4.x@PDP6	Descriptive Statistics Performance in G1 of the AIDAVA system.			
A2	Sum across patient arms for G2	Descriptive Statistics			

Computed	Description of measures	Test & meaning (per H1)
	A2.M1 = M1@PDP5 + M1@PDP7 A2.M2.x = M2.x@PDP5 + M2.x@PDP7 A2.M3.x = M3.x@PDP5 + M3.x@PDP7 A2.M4.x = M4.1@PDP5 + M4.x@PDP7	Performance in G2 of the AIDAVA system.
A3	Difference in A1 and A2 (i.e. difference between G1 and G2 across all patients)	Unpaired t-test
	Α3.Μ1-Δ = Α1.Μ1 - Α2.Μ1	H1: G2 more usable than G1
	A3.M2.xΔ = A1.M2.x - A2.M2.x A3.M3.x-Δ = A1.M3.x - A2.M3.x	H1: G2 requires less time for curation than G1 H1: G2 enable curation with less human intervention than G1
	A3.M4.X-∆ = A1.M4.x - A2.M4.x	Wilcoxon signed-rank test H1: The NLP system developed in G2 yields a higher precision than the NLP system from G1. H1: The NLP system developed in G2 yields a higher recall than the NLP system from G1.
A4	Difference in P1 and P2 (difference between the 2 patient arms)	Unpaired t-test (effect on training/experience) There is a difference in performance due to training/experience with the system : patients having used G1 are more/not more effective in G2 than patients who work with only one generation of the prototype (G1 or G2)
	Α4.Μ1-Δ = P1.Μ1-Δ - P2.Μ1-Δ	H1: G2 more usable than G1 (due to experience during G1)
	A4.M2.x-Δ = P1.M2.x-Δ - P2.M2.x-Δ A4.M3.x-Δ = P1.M3.x-Δ - P2.M3.x-Δ	H1: G2 requires less time for curation than G1 as patients are more experienced H1: There are less questions of the system unanswered during G2 than in G1 as the patient acquired experience in G1
	A4.M4	Not useful

Secondary Endpoint(s) Analysis

Description of measures	Test & meaning (per H1)
Breast Canc	er
Difference in data points 0 and 1 (i.e. difference between G0 and G1 across a sample of 15 patients) U0.TBCx- Δ = TBCx@SDP0 - TBCx@SDPA U0.EBCx- Δ = EBCx@SDP0 - EBCx@SDP1 U0.ACCx- Δ = ACCx@SDP0 - ACCx@SDP1	Unpaired t-test H1: G2 has more (or same) accuracy than G1 while keeping the same time saving and duration
	Descriptive Statistics around performance in G1 of the AIDAVA system (e.g. mean,)
Difference in data points 1 and 2 (i.e. difference between G1 and G2 across all patients) U1.TBCx- Δ = TBCx@SDP1 - TBCx@SDP2 U1.EBCx- Δ = EBCx@PSP1 - EBCx@SDP2 U1.ACCx- Δ = ACCx@SDP1 - ACCx@SDP2	Paired t-test H1: G2 has more (or same) accuracy than G1 while keeping the same time saving and duration
Cardiovascu	lar
	Descriptive Statistics around performance in G1 of the AIDAVA system (e.g. mean,)
Difference in data points 1 and 2 (i.e. difference between G1 and G2 across all patients) U1.TCVD- Δ = TCVD@SDP1 - TCVD@SDP2	Paired t-test H1: G2 has more (or same) accuracy than G1 while keeping the same time saving
	Description of measures Breast Canc Difference in data points 0 and 1 (i.e. difference between G0 and G1 across a sample of 15 patients) U0.TBCx- Δ = TBCx@SDP0 - TBCx@SDPA U0.EBCx- Δ = EBCx@SDP0 - EBCx@SDP1 U0.ACCx- Δ = ACCx@SDP0 - ACCx@SDP1 Difference in data points 1 and 2 (i.e. difference between G1 and G2 across all patients) U1.TBCx- Δ = TBCx@SDP1 - TBCx@SDP2 U1.EBCx- Δ = EBCx@PSP1 - EBCx@SDP2 U1.ACCx- Δ = ACCx@SDP1 - ACCx@SDP2 Cardiovascu Difference in data points 1 and 2 (i.e. difference between G1 and G2 across all patients) U1.TCVD- Δ = TCVD@SDP1 - TCVD@SDP2 U1.ACCyD- Δ = ACVD@SDP1 - ACVD@SDP2 U1.ACCyD- Δ = ACVD@SDP1 - ACVD@SDP2

